PeerFIT Intervention: The 12-month PeerFIT intervention consists of a 6-month intensive phase including: (a) once weekly 90-minute group weight management and exercise session led by a lifestyle coach; (b) once weekly one-hour physical activity session delivered in community settings; and (c) Facebook and mHealth technology (i.e., Fitbits, text messaging support) to increase motivation and facilitate self-monitoring and peer social support for health behavior change. Participants then transition to a 6-month lower intensity phase in which the 90-minute weight management sessions are discontinued. During the low intensity phase, participants will have continued access to the physical activity sessions, social media, and mHealth support described below. A total of 10-18 participants will be enrolled in each of the in-person groups with participants from all groups invited to join the secret PeerFIT Facebook group. The groups will be conducted as open groups with a minimum of 2 and maximum of 18 participants at any given time to offer more diversity and perspective from peer members. After 2 participants are enrolled, each new participant who joins the group will receive an orientation called the “Start Up Session” prior to the group session. The orientation session will be done individually or in a small group setting. The orientation session will last about one hour and will be conducted within one week prior to joining an existing PeerFIT group when possible.

Weight Management and Exercise Sessions. The PeerFIT weight management and physical activity component is adapted from the evidence-based Diabetes Prevention Program designed for individuals at risk for diabetes and cardiovascular disease in the general population. PeerFIT goals are to achieve 5% weight reduction and to increase physical activity gradually to 150 minutes per week over a 6-month period. A private and confidential weigh-in is conducted at the beginning of each session to track participants’ progress. Participants are taught to achieve their weight loss and fitness goals by lowering calorie intake by reducing their consumption of sugar-sweetened beverages and junk foods that are high in sugar and fat and eating fewer processed foods, while adding more fruits and vegetables and lean protein into their diets, and by

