participating in moderate-intensity physical activities. Daily self-weighing and physical activity trackers are used as self-monitoring strategies to promote and reinforce desired behavioral changes. Each 90-minute session includes up to 30-minutes of light to moderate physical activity (e.g., brisk walking) and weight management education and experiential learning activities taught at a beginner level. The PeerFIT lifestyle coach will be trained to deliver basic exercise instruction in a group format for overweight and obese young adults (e.g., walking groups). A certified fitness trainer will be hired as a consultant to the program 1-2 hours per month to develop a structured protocol for conducting the physical activity sessions and provide ongoing supervision for the lifestyle coach. The lifestyle coach will also be trained to lead team building activities, games, and problem solving exercises.

Physical Activity Sessions. In addition, we will offer a one-hour physical activity session each week delivered in community settings over the 12-month study. Due to the current COVID19 social and physical distancing guidelines, the weekly exercise sessions will be moved from community settings to an online format using Zoom technology during the social and physical distancing period. Participants currently enrolled in the study and randomized to the PeerFIT intervention will be notified of this change in the format of the intervention. At the beginning of each week, the PeerFIT coach will call each participant individually to invite them to join the group exercise session. If the participant expresses interest in joining the group the PeerFIT coach will send them Zoom meeting information via text message. This group will follow the same format each week consisting of a warm up, physical activity and cool down lasting no longer than 60 minutes. The group leader and program participants will decide together which activities to pursue each week (e.g., team sports, walking/jogging group, dancing, scavenger hunt). In the event the social and physical distancing restrictions are lifted at the agency prior to the end of this study, the PeerFIT coach may decide to resume conducting the exercise sessions in person.

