Comparison Condition: Basic Education supported by wearable Activity Tracking (BEAT)

Participants in the comparison condition will receive monthly individual lifestyle sessions delivered by a lifestyle coach including education, guidance, and support for self-monitoring behaviors (i.e., daily self-weighing and tracking daily steps) during the first six months of the study, plus text message reminders and encouragement for self-monitoring weight loss behaviors (3-5 text messages per week) during the entire 12-month study period. During the initial session, information about psychiatric medications and health behaviors associated with obesity in young adults with mental illness are presented as well as information about the role of healthy eating and exercise in improving physical health and mental health outcomes. Self-monitoring behaviors including daily self-weighing and physical activity monitoring are introduced as strategies for weight loss and increasing cardiovascular fitness. Participants will receive materials with tips and strategies for healthy eating and increasing physical activity. They will also be given a wearable activity tracker (i.e., Fitbit Zip, Flex 2, or Inspire) to use throughout the study with instructions for using the device and connecting it with their personal smartphone, tablet, or computer. The Fitbit Zip and Inspire are equipped with an LCD display that can be used to observe daily step counts without connecting to a smartphone or computer if participants do not own one. The Fitbit Flex 2 indicates progress towards step goals with LCD lights that light up on the wrist band, and more data such as exact steps can be monitored through the Fitbit app on participants' phones. Participants in the comparison condition will also receive routine access to technical assistance for using the Fitbit during the

monthly lifestyle sessions. The lifestyle coach providing the sessions will make sure the Fitbit is working properly, answer any questions about the device, and show participants how to check their progress by synching the Fitbit to a personal computer or smartphone. Participants may contact the lifestyle coach during business hours for one-on-one phone based technical assistance for using the device, but no active assistance is provided during these telephone contacts for behavioral strategies for weight loss.

Study Sites.

Mental Health Center of Greater Manchester (MHCGM)

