Qualitative interviews: At the 12-month assessment, a subset of study participants will be invited to participate in a one-time telephone interview exploring their experiences participating in the intervention (either BEAT or PeerFIT). We will purposively sample participants based on their participation in the intervention as either “no engagement,” “low engagement,” or “high engagement.” “No engagement” is defined as not attending any intervention sessions (PeerFIT or BEAT) during the 6-month intensive phase of the study. “Low engagement” is defined as attending less than 50% of the intervention sessions during the 6-month intensive phase. “High engagement” is defined as attending 50% or greater of the intervention sessions during the 6-month intensive phase. The study PI, [name], will conduct these telephone interviews with up to 36 participants across three study sites (approximately 12 participants per category and per site): GNMHC, MHGM, and CMHA. The interviews will last approximately 45 minutes and will explore in depth engagement in the interventions, including participants’ perceptions, preferences, and experiences with the interventions and barriers and facilitators to participation, and will follow a semi-structured interview guide. Participants will be paid \$30 to complete the telephone interview. With participants’ permission, the interviews will be audio recorded and transcribed for data analysis.

Research interviewers will undergo comprehensive training on administration and rating of the study measures consistent with established procedures at Dartmouth. Reliability will be established prior to administration of the battery. The data collection supervisor ([name]) will lead a bi-weekly supervision meeting with the

interviewers to answer questions, monitor data collection and minimize rater drift. Assessments will include baseline and follow-up measures required for Aims 1 and 2 as well as participant characteristics and covariates, as displayed in Table 1. Note: Participants' weight will be taken on day 1 of treatment for both conditions and this value will be used as the participant's baseline weight. Participants' baseline BMI will be calculated based on this value.

Table 1. Study Variables and Measures for Aims and Hypotheses

Physical Measures	Instrument	Source	0	6	12	
Height	Stadiometer	Interviewer	✓			Stadiometer
Weight	Digital Scale	Interviewer	✓	✓	✓	Digital Scale

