To monitor study recruitment and enrollment, the PI ([name]) will lead a weekly supervision call with the research coordinator and research interviewers to monitor progress and regularly address questions and problems that arise during recruitment. Our approach to assessing data quality includes: 1) monitoring counts of completed data collection items; 2) monitoring distribution of trial outcomes, overall, by data collector and site; 3) record lag time in data entry; 4) issue queries on missing data, out of range values or illogical data relations; and 4) review types and distribution of data entry errors. Weekly research team conference calls, including assessment supervision, will help identify quality control issues early and allow consensus solutions to be reached.

Data Safety and Monitoring Plan: Although there is a low risk of adverse events (AE) associated with gradual, supervised weight loss and moderate exercise in young adults, an independent data safety monitoring process will be implemented for the proposed clinical trial. An independent Data Safety Monitoring Board (DSMB) will conduct reviews of the study every 12 months to ensure the safety of participants and data validity and integrity. The established DSMB that will be used for this study consists of several federally funded, highly experienced clinical researchers in the Department of Psychiatry at the Geisel School of Medicine at Dartmouth. Current members of the DSMB consist of researchers who are not co-investigators or collaborators on this proposal. This independent board will follow the policy for data and safety monitoring published by NIH.

The DSMB will be responsible for reviewing the following information: adverse consequences (whether serious or minor) to any participant and actions taken to remedy the problem; data quality, completeness, timeliness; performance of the study site; recruitment and retention; adherence to protocols; maintenance of confidentiality; external factors impacting safety or ethics of the study; and new or evolving information regarding the expected effectiveness and/or safety of the PeerFIT intervention. Summary reports of the meetings will be sent at the time of annual reviews to the Dartmouth Committee for the Protection of Human Subjects (CPHS).

6. Risks & Benefits

Note: Risks may be physical, psychological, social, legal, economic, to reputation, or others.

a. Describe any potential risks, their likelihood and seriousness:

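### No listed assessment asks about adverse events in either arm, and the incidental contact that might reveal them is far more frequent in PeerFIT (78 scheduled sessions) than in BEAT (6)

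*Combined protocol and SAP*

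**What the plan says.** **Oversight.** Under section 5, Data Safety and Monitoring Plan, an independent board "will conduct reviews of the study every 12 months to ensure the safety of participants and data validity and integrity". Its remit includes "adverse consequences (whether serious or minor) to any participant and actions taken to remedy the problem" and new information on the safety of PeerFIT.

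**Data collection.** Section 3, Data Collection and Measurement, says the assessments cover the "measures required for Aims 1 and 2 as well as participant characteristics and covariates, as displayed in Table 1". Blinded interviewers see both arms at baseline, 6 and 12 months.

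**PeerFIT contact.** The first six months include a "once weekly 90-minute group weight management and exercise session led by a lifestyle coach". A "6-month lower intensity phase in which the 90-minute weight management sessions are discontinued" follows. In addition, "we will offer a one-hour physical activity session each week delivered in community settings over the 12-month study".

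**BEAT contact.** Participants receive "monthly individual lifestyle sessions delivered by a lifestyle coach", and these run "during the first six months of the study". Both arms receive 3 to 5 text messages per week for 12 months.

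**Unexpected events.** Section 7 recognises that such events may come up in group sessions or research interviews. It has the intervention staff or the research team alert the on-site clinical team, and it passes unexpected research findings to the site PI.

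**The concern.** The board is asked to judge adverse consequences in any participant, but the plan describes no step at which participants are asked about them. What the board receives then depends on how often someone from the study happens to be in touch with the participant, and that differs greatly by arm.

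Two things are at stake. First, completeness: events in BEAT participants, and in PeerFIT participants who no longer attend, may never be recorded. Second, interpretation: if event counts are laid out by arm, an excess in PeerFIT could reflect true harm or simply closer observation, and the data would not separate the two.

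**Working it through.** The plan gives no adverse-event rate, safety sample size or contact total, so there is no stated figure to reproduce. The check has two parts: what is collected, and how often each arm is seen.

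**1. Is there an adverse-event item anywhere in the listed data collection?**
- Table 1: physical, dietary, activity and psychosocial measures, other questionnaires and treatment covariates. No adverse-event, injury, emergency-visit or hospitalisation item.
- Section 3.6.2, measure descriptions: none. The nearest items are the CES-D, the medication review, weight and blood pressure. None of these asks about injury, hospital care or cardiac symptoms.
- Section 3, Fidelity Measurement: content, activities, delivery method and attendance only.
- Section 5: no event definition, seriousness grading, recording form, reporting timeline or tabulation by arm.

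Part of the study-site descriptions is not in the available text and could not be checked.

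**2. Scheduled sessions per participant** (26 weeks = 6 months, 52 weeks = 12 months)

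| Period | PeerFIT | BEAT |
|---|---|---|
| Months 1–6 | 26 × 1 weight management + 26 × 1 exercise = 52 | 6 × 1 = 6 |
| Months 7–12 | 26 × 1 exercise = 26 | 0 |
| Total | 78 | 6 |

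Ratio: 78 / 6 = 13. With 4-week months it is (24 + 48) / 6 = 72 / 6 = 12. Adding the PeerFIT start-up session gives 79.

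**3. Safety-relevant contacts described for PeerFIT only**
- A coach's weigh-in at each weight-management session, with an interview after sudden marked weight loss (section 6, Nutrient intake).
- Facebook monitoring at least three times a week (section 13).
- Unblinded telephone assessments at 6 and 12 months (section 3).
- A weekly individual call from the coach while exercise sessions are held online (section 3, Physical Activity Sessions).

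**4. Contacts common to both arms**
- Two follow-up assessments by blinded interviewers, without an adverse-event question.
- Texts: 3 × 52 = 156 to 5 × 52 = 260 per participant. If each text counted as much as a session, the ratio would be (78 + 156) / (6 + 156) = 234 / 162 = 1.4, or (78 + 260) / (6 + 260) = 338 / 266 = 1.3. As described, the texts carry reminders and encouragement, not safety questions.

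**5. Illustration only.** Assume full attendance, events spread evenly over 12 months, no detection outside sessions, and an event mentioned only if a session follows within w weeks. Weekly sessions then cover all PeerFIT events. The share covered in BEAT is 0.5 × min(1, w / (52/12)).

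| Assumed w (weeks) | BEAT share | Apparent PeerFIT:BEAT ratio with equal true rates |
|---|---|---|
| 1 | 0.115 | 8.7 |
| 2 | 0.231 | 4.3 |
| 4 | 0.462 | 2.2 |
| 8 | 0.500 | 2.0 |

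The result is set by the assumed window. It shows the direction of the problem and gives no estimate of its size.

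**6. With the change proposed below.** Scheduled enquiries about adverse events become 2 in PeerFIT and 2 in BEAT.

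**The case against.** **Coaches are not the only route.** A reader might infer that the board learns only what coaches happen to hear. The documents do not support that. Section 7 names research interviews and the research team, section 9d has concerns about any participant discussed on weekly supervision calls, and participants are clients of the study agencies. This stands. But these provisions escalate events to clinical staff and site or study PIs; they add no question and state no route to the board.

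**The plan makes no safety comparison.** A reader might also infer that a planned comparison is biased. No aim, hypothesis or analysis compares events by arm, and the board's remit reads as review of individual events. This stands, so the comparability problem is conditional on counts being viewed by arm. The incompleteness is not conditional in that way.

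**Table 1 lists research variables.** It does not claim to list safety forms, and the board follows an NIH monitoring policy that the plan does not reproduce. The point is therefore limited to listed assessments.

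**The 13:1 ratio is selective.** The 78 and 6 are sessions offered, not attended, and leave out texts, BEAT participants' access to the coach by phone, and the assessments held in both arms. This stands as a caution. However, the phone access is for technical help with the device. Low attendance does not cure the gap; it adds PeerFIT non-attenders to those out of view.

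**Risk is low.** Section 5 says so. Section 6, however, rests its reassurance on young adults without a prior cardiac event, while the eligibility table admits some people with cardiac or eating-disorder histories after medical clearance. The premise does not cover everyone enrolled.

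**Conclusion.** The point holds in this form. No listed assessment elicits adverse events in either arm, and detection rests on incidental reporting. Scheduled sessions are 78 in PeerFIT and 6 in BEAT (26 and 0 in months 7 to 12), and several further contacts that could reveal events are described for PeerFIT only. The board's event information would be incomplete for BEAT and for PeerFIT non-attenders, and counts would not be comparable if viewed by arm.

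The session counts follow from the plan's schedule and describe offered contact. A definite two-fold or larger false excess in PeerFIT should not be read into them: the 2.0- to 8.7-fold range comes wholly from assumed mention windows, and the documents do not allow the distortion to be sized. The conclusion also assumes that no separate safety form exists outside the listed measures. No efficacy analysis is affected. The change is still worth making, because the board's stated task cannot be met evenly across arms by the procedures described.

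**What to change.** Add a short adverse-event checklist to the remaining 6- and 12-month interviews in both arms. It could cover, for example, injury, emergency visit, hospitalisation, cardiac symptoms and eating-disorder symptoms. The wording should be identical in the two arms and usable by phone, since assessments may be done that way under the COVID-19 restrictions. Ask it after all outcome measures.

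Report these solicited events to the board by arm, separately from incidentally reported ones, and note the unequal contact when interpreting the latter.

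**Cost.** A minor amendment and a few minutes per existing interview; no new visits or staff. Six-month recall of minor events will be imperfect. There is a small risk that an answer reveals the arm. Asking last protects that visit's measures, but not the 12-month measures if the same interviewer takes them after hearing a 6-month answer. This version is dated May 2020, so some interviews may already be past. Those participants' earlier events would not be recovered in full, and reports to the board should say so.

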This randomized controlled trial will be conducted in real-world mental health settings providing services to clients within the Massachusetts Department of Mental Health (DMH) community-based system of care, the Mental Health Center of Greater Manchester (MHCGM) in Manchester, NH, the Greater Nashua Mental Health Center of Community Council (GNMHCCC) in Nashua, New Hampshire, and the Community Mental Health Affiliates (CMHA) in New Britain, CT. A total of 144 young adults with SMI and overweight/obesity (BMI ≥ 25) will be recruited from the MHCGM, GNMHCCC, and CMHA, as well as from sites within DMH to participate in a randomized controlled trial. The study will be referred to as the “Fit Forward Lifestyle Trial for in Young Adults.” Participants will be randomized 1:1 to PeerFIT or to Basic Education in fitness and nutrition supported by a wearable Activity Tracking device (BEAT), resulting in approximately 72 clients randomized to PeerFIT and 72 clients randomized to BEAT. Recruitment will occur on a rolling basis with the PeerFIT group intervention starting once at least 2 new people have been randomized to PeerFIT. Thus, we will run open PeerFIT groups in which up to 18 new members are welcome to join at any time during the life of the group. The BEAT individual intervention will begin as soon as 2 participants are randomized to that intervention. This rolling recruitment process combined with open PeerFIT groups is an adaptation to the study design intended to reduce the participant burden of waiting to start the intervention until a full cohort of participants is recruited, which typically takes many months.

INTERVENTION AND CONTROL CONDITION

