Fitbit Wearable Activity Trackers. Participants are provided Fitbit Zip, Flex 2, or Inspire wearable activity trackers for self-monitoring physical activity and instructions for downloading the free Fitbit mobile application to track progress over time. Participants will be provided with basic smartphones to access the Fitbit mobile application if they do not own a smartphone. The Fitbit Zip (see Figure 1A) is a wearable accelerometer that clips onto clothing and tracks number of steps walked each day. Participants can view their steps on the LCD display and connect wirelessly to the mobile application to track their

Figure 1A. Fitbit Wearable Activity Tracker

Figure 1B

progress over time and earn rewards for reaching daily step goals. The Fitbit Flex 2 and Fitbit Inspire is worn as a wristband and also tracks number of steps each day. As a wristband, it is hard to misplace and it is also waterproof. Step goals are set through the Fitbit app and progress towards those goals can be tracked by the number of LCD lights that light up on the wristband of the Flex 2. Other progress can be checked on the Fitbit app. Participants can also compare steps and progress by connecting with each other through the mobile application. In our pilot work participants expressed high satisfaction with using the Fitbit Zip, found it easy to understand, and valued using it to track their steps each day.

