Power Analysis for Aim 1. Assuming a range of within-person, across time correlations (0.1-0.7), with 144 participants (72 per arm), there will be 80% power, at the two-sided 0.05 significance level, to detect a difference between arms in slope of at least 0.030-0.052 SD units per month, or equivalently, 0.36-0.62 SD units over 12 months. If SDs of weight, BMI, and 6-MWT are similar to those observed previously (approximate weight SD 60, BMI SD 9, and 6-MWT SD 350) with the InSHAPE intervention and active control, these standardized effect sizes are equivalent to difference between arms of 21.6-36.0 lbs, 3.20-5.40 BMI units, and 6-MWT of 126-210m over 12 months. With attrition, power will be slightly lower, or equivalently, detectable differences slightly larger. To provide information on detectable differences if maximum attrition is experienced we also provide detectable differences assuming data from only 115 participants (80% of proposed sample size). In this case, the detectable difference increases to 0.034-0.059 SD units per month or 0.41-0.70 over 12 months yielding detectable weight of 24.6-42.0 lbs, BMI of 3.69-6.30, and 6-MWT of 143-245m over 12 months. True power/detectable difference likely lies in between for 144 vs. 115 participants. In the InSHAPE trial, 38% of participants in the active control arm and 51% of participants in InSHAPE achieved a clinically significant change in cardiovascular risk reduction. Because InSHAPE likely had a strong intervention effect with one-on-one personal fitness training and a gym membership for the active control, we estimate that percentages achieving clinically significant change in cardiovascular risk reduction in this study will be 20% for BEAT and 40% for PeerFIT. Assuming these proportions, there will be 86% power to detect a difference between arms in cardiovascular risk reduction, assuming measures of this outcome at 2 time points and within-person correlation of 0.5. With maximum attrition, the power is reduced to 77%.

Specific Aim 2 (Mechanism of Action): To test the mechanism hypotheses, parallel process latent growth curve models will be fit within a structural equation model (SEM) framework. These models allow for testing mediation of the treatment effect on weight and fitness by changes in self-efficacy (H2a) and peer social support (H2b). It is hypothesized that PeerFIT will have a greater effect on the change over time (slope) of

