Fitbit activity tracker. The Fitbit activity tracker poses minimal, if any, risks to participants. The device is worn on the wrist or by attaching it to participants' clothing, or keeping it in participants' pockets, and is designed to monitor steps walked and overall participation in physical activity. The device itself does not collect or contain any personal information. Each participant will create an online Fitbit account that will only contain participants' names, email address (which is their Fitbit username), gender, age, height, and weight. No other personally identifying information regarding each participant is stored within the online profile. Individual usernames and passwords for the online profile will only be known by research staff and respective participants. Fitness data will be collected from the device over a secure electronic connection and will be stored in the user's online account that synchs with the device through the smartphone application. Participants will also have the option to use other features on the Fitbit smartphone application such as viewing physical activity over time, tracking sleep, or tracking dietary intake. Using the app is optional but encouraged. Research members will not share Fitbit data from participants with other study participants. However, participants can choose to connect with other participants using the Fitbit smartphone "friend" feature built into the Fitbit app to share information such as step count and distance traveled. Participants can also choose to share their steps or progress meeting their step goals with other participants using the secret Facebook group.

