In addition to these traditional recruitment methods, we will use novel channels and venues to recruit young adults with SMI. **First**, information about the study will be posted to the Vinfen, MHCGM, and CMHA Facebook groups. **Second**, we will equip 3-4 peer providers at each site with Fitbits to demonstrate and role model the use of the devices, which may incentivize young adults to learn more about the study. **Third**, we will

use experiential marketing strategies involving a series of live events with music and fun and engaging activities to give members of the target audience opportunities to experience firsthand the mobile technology used in the study. Healthy and flavorful foods will be served at each event and young adult clients will have the opportunity to socialize with one another, see a Fitbit demonstration and tryout the device for themselves, pick up “Fit Forward” branded giveaways like pens and wristbands, and win door prizes (e.g., water bottles or gym bags). Finally, young adults who enroll in the study will have the opportunity to refer other young adults in their social networks who also receive services at the study sites.

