In addition, the lifestyle coaches will have continuous access to the secret Facebook group through their study smartphones. The lifestyle coaches will be provided with smartphones connected to the Facebook application so that they can easily access the secret Facebook group and view content or respond to participants' posts. The lifestyle coaches' smartphones will be setup to receive automatic updates and push notifications whenever any content or comments are posted in the secret Facebook group. The lifestyle coaches will be instructed to check the notifications and content posted in the Facebook on a daily basis (Mon-Fri). The lifestyle coaches will be instructed to follow a protocol where they will inform study staff immediately if participants post any hurtful, derogatory, or inappropriate content. The lifestyle coaches will be instructed to call 911 immediately and to also contact the study staff in the unlikely event that a participant posts comments related to self-harm or harming others. In our prior experiences using Facebook as part of the PeerFIT program, we have not had any concerns related to the content or types of posts from participants. Participants in this study can use their personal Facebook account to join the secret PeerFIT Facebook group. Use of the secret group feature will minimize any risk of a loss of privacy experienced by sharing personal information with other participants. Participants will also be asked not to share any information or content posted in the secret Facebook group with people who are not enrolled in the intervention arm of the study. The secret Facebook component of the PeerFIT program is entirely voluntary, and participants can choose to stop using the Facebook group at any time, or they can choose to use it as often or as little as they would like.

14. Confidentiality of Data

Note: Any person engaged in research collecting information about illegal conduct may apply for a [Certificate of Confidentiality](#) from the National Institute of Health.

a. If disclosed, could any of the data collected be considered sensitive, with the potential to damage financial standing, employability, insurability, or reputation?

X No Yes

If Yes, describe the data or information, the rationale for their collection, and whether a Certificate of Confidentiality will be obtained:

b. Describe the safeguards employed to secure, share, and maintain data during the study, addressing any of the following which may apply:

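### Fitbit friend links between participants are not limited by arm, so a small part of the PeerFIT peer component may reach BEAT

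*Combined protocol and SAP*

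**What the plan says.** Section 3 gives a Fitbit Zip, Flex 2 or Inspire to both arms (the BEAT description and the Fitbit paragraph under treatment-related covariates). Within the PeerFIT technology component, the paragraph on wearable trackers says: "Participants can also compare steps and progress by connecting with each other through the mobile application". The BEAT description offers individual coaching, a tracker, technical help and text messages. It neither offers nor forbids linking with other participants.

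The Fitbit paragraph of section 6a (Risks) covers the device generally. It says "participants can choose to connect with other participants using the Fitbit smartphone" friend feature to share step counts and distance. It names no arm, and it describes app use as optional but encouraged.

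The only cross-arm limit found concerns Facebook. Section 13 (Privacy) says "Participants will also be asked not to share any information or content posted in the secret Facebook group" with people outside the intervention arm. No matching request covers Fitbit links.

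**The concern.** The contrast between PeerFIT and BEAT rests partly on peer contact: PeerFIT is a group programme and BEAT is individual. If a BEAT participant links devices with a PeerFIT participant, some of that contact crosses the arms.

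Such links are plausible for three reasons:
- Participants receive services at the same centres and are randomised individually.
- Section 10 (Recruitment) says "young adults who enroll in the study will have the opportunity to refer other young adults in their social networks", so acquaintances can be allocated to opposite arms.
- Section 10 also describes group orientation sessions before randomisation, where people later allocated to different arms can meet.

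The links would leave no trace in the study's Fitbit data, since section 6a states that Fitabase does not retain the friends list. What is at stake is some power for Aim 1. If the result is null, there would also be some doubt about whether the contrast was slightly diluted.

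**Working it through.** **Inputs, from the Aim 1 power analysis in section 3.6.5 except where noted**
- Alpha: "at the two-sided 0.05 significance level". This is stated for the slope calculation; I assume that it carries over to H1b.
- Sample: "with 144 participants (72 per arm"); 115 in total under maximum attrition, so 57.5 per arm. Allocation (section 3, Design Summary): "Participants will be randomized 1:1 to PeerFIT or to Basic Education in fitness and nutrition".
- H1b response rates: "will be 20% for BEAT and 40% for PeerFIT".
- Two time points (m = 2) and within-person correlation ρ = 0.5.
- Stated power: 86%, and 77% with maximum attrition.
- Leakage to BEAT: not given in the documents; assumed below.

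**Step 1: reproduce the plan's power**

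Effective n per arm = n / [(1 + (m − 1)ρ)/m]. The divisor is (1 + 0.5)/2 = 0.75, so 72/0.75 = 96 and 57.5/0.75 = 76.7.

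Power = Φ{(Δ − 1.96 × SE0)/SE1}, where SE0 = √[2p̄(1 − p̄)/n] and SE1 = √[(p1(1 − p1) + p2(1 − p2))/n].

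With p1 = 0.20, p2 = 0.40, p̄ = 0.30 and n = 96:
- SE0 = √(0.42/96) = 0.0661
- SE1 = √(0.40/96) = 0.0645
- (0.20 − 1.96 × 0.0661)/0.0645 = 1.09, so power = 86.2% (plan: 86%)

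With n = 76.7, SE0 = 0.0740 and SE1 = 0.0722. The argument is 0.76 and power = 77.7% (plan: 77%). Both stated figures reproduce to within one point, and both assume no leakage.

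**Step 2: add leakage**

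Let d = (share of BEAT linked across arms) × (share of the PeerFIT effect that such a link carries). The BEAT rate becomes 20% + d × 20 points, with PeerFIT held at 40%.

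| d (assumed) | BEAT rate | Power, 144 | Power, 115 |
|---|---|---|---|
| 0 | 20.0% | 86.2% | 77.7% |
| 2% | 20.4% | 84.6% | 75.8% |
| 5% | 21.0% | 82.1% | 72.8% |
| 10% | 22.0% | 77.4% | 67.7% |

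For scale, 20% of BEAT linked across arms with each link carrying 10% of the effect gives d = 0.20 × 0.10 = 2%. Reaching 10% would need, for example, half of BEAT linked with each link carrying a fifth of the effect (0.50 × 0.20).

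**The case against.** The strongest reply is that section 6a is loosely worded and may not be meant as permission for BEAT. Its next sentence on sharing says participants can post their steps in the secret Facebook group, which only PeerFIT can join. Step comparison is otherwise described only for PeerFIT. Exposure in BEAT may also be low: the app is optional, study smartphones are described only for PeerFIT, and BEAT sessions are individual. This stands in part. It argues for a small leakage and for careful wording, but the ambiguity is itself a reason to state who may link with whom.

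A reader might go further in four ways that the documents do not support.
- **That step comparison defines PeerFIT.** Section 3 builds PeerFIT from a weekly group session, a weekly activity session, Facebook and mobile support. A linked BEAT participant still receives no group sessions, activity sessions or Facebook group.
- **That power could collapse.** At d = 20% or 30%, H1b power with 144 participants would be 66% or 54%. That would require, for example, 20% or 30% of BEAT to gain the full PeerFIT effect from seeing step counts, and nothing in the plan suggests this.
- **That the peer-support mediation test in Aim 2 is weakened by these links.** Table 1 lists the Social Provisions Scale for PeerFIT only, and it rates support from group members, so BEAT has no score for a link to raise. The both-arm MOS survey covers general support, and nothing in the plan indicates that step sharing would move it.
- **That links between BEAT participants are contamination.** They do not cross arms. Whether the tracker's built-in features belong to the comparator is a design preference.

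**Conclusion.** The concern holds in a limited form. Both arms have the device, the plan allows friend links without naming an arm, the same function is presented as a PeerFIT feature, and no safeguard like the Facebook request was found for Fitbit. Cross-arm links are plausible and would not appear in the Fitbit data, but the documents do not show that they will occur or how often.

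The expected consequence is a modest bias toward no difference in Aim 1. Under assumed leakage of 2% to 10%, H1b loses about 2 to 9 points of power at 144 participants (86.2% to 84.6% or 77.4%). At 115 participants it loses about 2 to 10 points (77.7% to 75.8% or 67.7%). The lower end is the more plausible, since step comparison is one optional feature. The sizes rest on the plan's own 20% and 40% rates, on the carried-over alpha, and on a leakage range that the documents do not supply. Part of the site descriptions was not in the text examined, so a safeguard stated there cannot be excluded.

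**What to change.** Reword the Fitbit paragraph in section 6a, and whatever script is used at the Visit 5 technology set-up, so that friend linking is offered as a PeerFIT feature among PeerFIT participants. Ask participants in both arms not to link with participants in the other arm, mirroring the Facebook request in section 13.

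The cost is a sentence or two in the protocol and the set-up script. The request cannot be enforced, and it slightly restricts an optional app feature.

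I would not add a recording of links at 6 and 12 months for a sensitivity analysis. The unblinded telephone interview exists only for PeerFIT and BEAT coaching sessions end at six months, so 12-month recording in BEAT would need a new unblinded contact. Linking is also self-selected after randomisation, so a comparison by link status would be confounded by engagement.
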